4. STUDY DESIGN

This will be a Phase I, randomized, double-blind, double-dummy, placebo-controlled, positive-controlled, multi-site, 3-arm study to investigate the effects of therapeutic and supratherapeutic oral doses of CBP-307 on the QTc interval in healthy male and female subjects.

Potential subjects will be asked to read and sign an informed consent form (ICF). After informed consent is obtained, screening procedures and tests to establish subject eligibility to enter the study will be performed within 28 days before Day 1. After informed consent has been obtained but prior to the initiation of study treatment administration, only SAEs will be reported. After placebo administration to all subjects on Day -1, all AEs, whether volunteered, elicited, or noted upon physical examination, will be recorded throughout the study (ie, from Day -1 until the end of the study).

In this study, approximately 68 healthy subjects (at least 30% for each sex) will be randomized into 2 groups (Group 1 and 2) with 34 subjects in each. Group 2 consists of 2 sub-groups (Group 2A and 2B) and each sub-group will be randomized with 17 subjects. Randomized subjects will receive the assigned study drug as a single dose in the morning on Days 1, 2, 3 to 6, 7 to 15, and on Day 16 (placebo will be administered to all subjects on Day -1).

The following treatments will be administered:

- Starting doses of CBP-307 for titration (0.05 mg on Day 1 followed by an up-titrated dose of 0.1 mg on Day 2)
- A therapeutic dose of CBP-307 (0.2 mg, Days 3 to 6)
- A supratherapeutic dose of CBP-307 (0.5 mg, Days 7 to 15)
- Placebo (matched to moxifloxacin and CBP-307)
- Moxifloxacin (400 mg)

Moxifloxacin will be used as a positive control to determine the assay sensitivity of this study with an expected peak QT effect (placebo-corrected change-from-baseline QTcF; $\Delta\Delta QTcF$) of 10 to 15 msec.

[figure not shown]
A summary of dosing timelines per Group is shown below:

Study Treatment Name	Treatment Group	CBP-307	CBP-307 Matched Placebo	Moxifloxacin (Avelox)	Moxifloxacin Matched Placebo
Dosage Formulation		Capsule	Capsule	Tablet	Tablet
Unit Dose Strength(s)/Level(s)		0.05 mg 0.1 mg	Not applicable	400 mg	Not applicable
Dosage Frequency					
Day -1	Group 1 Group 2A Group 2B		1 capsule 1 capsule 1 capsule		
Day 1	Group 1 Group 2A Group 2B	1 × 0.05 mg		1 × 400 mg	1 tablet 1 tablet
Day 2	Group 1 Group 2A Group 2B	1 × 0.1 mg			
Days 3 to 6	Group 1 Group 2A Group 2B	2 × 0.1 mg			

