Days 7 to 15	Group 1 Group 2A Group 2B	5 × 0.1 mg			
Day 16	Group 1 Group 2A Group 2B		1 capsule 1 capsule 1 capsule	1 × 400 mg	1 tablet 1 tablet

A schematic of the study design is presented in

[Figure 1.](#)

Figure 1: Study Design

Potential subjects will be screened to assess their eligibility to enter the study within 27 days prior to the first dose administration. Subjects will be admitted into the study site on Day -2 (or on Day -4 depending on the clinical site's requirement for Coronavirus Disease 2019 [COVID-19] testing) and will remain at the study site until discharge on Day 19. Treatment administration will occur on Days 1, 2, 3 to 6, 7 to 15, and 16 under fasting conditions (all subjects will receive placebo on Day -1). Continuous cardiodynamic ECG monitoring and recording will begin at least 25 hours prior to the administration of study treatments on Day 1 and continue through 24 hours after the administration of study treatments on Days 1, 6, 15, and 16 and at corresponding timepoints on the day before dosing, ie, Day -1. Blood samples for PK analysis will be collected predose and at each postdose cardiodynamic ECG timepoint. Additional PK samples will be collected at 72 and 96 hours following dosing on Day 15. Subjects will return to the study site for a follow-up visit on Day 29±2 days.

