8.6. Safety and Tolerability Assessments

8.6.1. Adverse Events

All AEs will be coded using the Medical Dictionary for Regulatory Activities (MedDRA) Version 24.0 (or higher if a new version is issued during the study; see the DMP for more details).

A treatment-emergent adverse event (TEAE) will be defined as an AE that starts during or after dosing on Day 1, or starts prior to dosing on Day 1 and increases in severity after each dosing.

A treatment related TEAE will be defined as a TEAE with a relationship of possibly related or related to the study treatment, as determined by the investigator.

All AEs will be listed. In addition to the data recorded in the database, the listings will include derived onset time and duration. Onset time will be calculated from the time of dosing for TEAEs only. Where the last associated dose is referring to the last dose received prior to the start of a TEAE.

The frequency of subjects with TEAEs and the number of TEAEs will be summarized for the following categories:

- TEAEs (overall, serious, leading to discontinuation, and leading to death) by treatment
- TEAEs by severity and treatment
- Treatment-related TEAEs (overall, serious, leading to discontinuation, and leading to death) by treatment
- Treatment-related TEAEs by severity and treatment

The frequency of subjects will be summarized separately for TEAEs and treatment-related TEAEs by the following:

- System organ class, preferred term, and treatment
- Preferred term and treatment

For the AE data the following rules will apply:

- For the derivation of treatment-emergent status (applicable to all AEs): The collecting time window for AEs will be from after the time of signing the ICF until end of study (EOS)
- For the derivation of treatment-emergent status (applicable to all AEs): If the start date/time of an AE is incomplete or missing, an AE will be assumed to be a TEAE, unless the incomplete start date/time or the end date/time indicates an AE started

before dosing. For the derivation of treatment-related status (applicable to TEAEs only): If the study treatment relationship for a TEAE is missing, a TEAE will be assumed to be a treatment-related TEAE.

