- For the derivation of onset time (applicable to TEAEs only): If the start date/time of a TEAE is missing, onset time will not be calculated. If the start date/time of a TEAE is incomplete, where possible, the minimum possible onset time will be calculated and presented in ‘ \geq DD:HH:MM’ format (eg, if the date/time of dosing is 01MAY2019/08:00 and recorded start date/time of a TEAE is 03MAY2019, then the minimum possible onset time will be calculated by assuming a TEAE started at the first hour and minute of 03MAY2019 [03MAY2019/00:00], thus will be presented as onset time \geq 01:16:00 in the listing). If the start date of a TEAE is the same as the date of dosing but the start time of a TEAE is missing, an onset time will be presented as ‘ \geq 00:00:01’. Any clock changes will be accounted for in the derivation.
- For the derivation of duration (applicable to all AEs): If the end date/time of an AE is missing, duration will not be calculated. If the start or end date/time of an AE is incomplete, where possible, the maximum possible duration will be calculated and presented in ‘ \leq DD:HH:MM’ format (eg, if the start of an AE date/time is 01MAY2019/08:00 and its recorded end date/time is 03MAY2019, then the maximum possible duration will be calculated by assuming an AE ended at the last hour and minute of 03MAY2019 [03MAY2019/23:59], thus will be presented as duration \leq 02:15:59 in the listing). Any clock changes will be accounted for in the derivation.
- For the calculation of TEAE summary statistics: If the severity of a TEAE is missing, that TEAE will be counted under the ‘missing’ category.
- For the calculation of TEAE summary statistics: Counting rules for TEAEs: The collecting time window for TEAEs will be from the time of dosing on Day 1 until study completion (Day 1~EOS).
 - For CBP-307 0.05mg dose, only count/collect/record TEAEs that starts or increases in severity during the dosing level of CBP-307 0.05mg (from the time of dosing 0.05mg on Day 1 until the start of dosing 0.1mg on Day 2), irrespective of the TEAE’s ending time.
 - For CBP-307 0.1mg dose, only count/collect/record TEAEs that starts or increases in severity during the dosing level of CBP-307 0.1mg (from the time of dosing 0.1mg on Day 2 until the start of dosing 0.2mg on Day 3), irrespective of the TEAE’s ending time.

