 - For CBP-307 0.2mg dose, only count/collect/record TEAEs that starts or increases in severity during the dosing level of CBP-307 0.2mg (from the time of dosing 0.2mg on Day 3 until the start of dosing 0.5mg on Day 7), irrespective of the TEAE’s ending time.

- For CBP-307 0.5mg dose, only count/collect/record TEAEs that starts or increases in severity from the time of dosing 0.5mg on Day 7 until study completion (Day 7~EOS), irrespective of the TEAE's ending time.
- For the calculation of TEAE summary statistics: If a subject experienced multiple TEAEs with the same preferred term for the same treatment, this will be counted as 1 TEAE for that treatment under the maximum severity recorded.

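### SAP Section 8.6.1 counts TEAEs by dose over windows of about 1, 1, 4 and 22 days and states no matching placebo or moxifloxacin window, so raw TEAE percentages mix dose with time at risk

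*SAP*

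**What the plan says.** SAP Section 8.6.1 lists the summaries as "TEAEs (overall, serious, leading to discontinuation, and leading to death) by treatment" and "TEAEs by severity and treatment", with the same breakdown for treatment-related events and for system organ class and preferred term. The counting rules then define a window for each CBP-307 dose:

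- 0.05 mg: "from the time of dosing 0.05mg on Day 1 until the start of dosing 0.1mg on Day 2"
- 0.1 mg: "from the time of dosing 0.1mg on Day 2 until the start of dosing 0.2mg on Day 3"
- 0.2 mg: "from the time of dosing 0.2mg on Day 3 until the start of dosing 0.5mg on Day 7"
- 0.5 mg: "from the time of dosing 0.5mg on Day 7 until study completion (Day 7~EOS"

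Section 4 gives the dosing period for the last level as "A supratherapeutic dose of CBP-307 (0.5 mg, Days 7 to 15" and fixes the end of observation: "Subjects will return to the study site for a follow-up visit on Day 29±2 days".

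For placebo and moxifloxacin, Section 8.6.1 states only the general TEAE window, from Day 1 dosing to end of study. Table 1 in Section 6 has one placebo label and one moxifloxacin label. Repeated events with the same preferred term under one treatment count once, at maximum severity. No rate per unit of exposure is mentioned.

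Sections 8.6.2 to 8.6.4 summarise laboratory values, vital signs and safety ECGs by group treatment sequence and timepoint. Section 6 also says in general terms that summaries follow planned treatment sequences, which does not agree with the by-treatment layout in Section 8.6.1.

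**The concern.** Safety and tolerability of therapeutic and supratherapeutic multiple doses is a stated secondary objective (Section 2). The planned AE percentages are the main summary for it, and they put 0.2 mg observed for 4 days beside 0.5 mg observed for about 22 days. More observation time gives more subjects with at least one event and, because repeats collapse to the maximum severity, more chance of a higher grade. A reader could take this for a dose effect.

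The design already contains a randomised control group observed on the same calendar days. The laboratory, vital-sign and ECG summaries keep that comparison. The by-treatment AE layout does not clearly do so. If the placebo column covers most of the study, the three lower doses could look safer than placebo simply because they were observed for less time.

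**Working it through.** The SAP gives no AE rate, power or sample size for the AE tables, so there is no figure of its own to reproduce.

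**Step 1: window lengths (Sections 4 and 8.6.1), in elapsed days.**

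- 0.05 mg: 2 − 1 = 1
- 0.1 mg: 3 − 2 = 1
- 0.2 mg: 7 − 3 = 4
- 0.5 mg: 29 − 7 = 22, with range 27 − 7 = 20 to 31 − 7 = 24

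From the Day 7 dose to the Day 16 dose is 16 − 7 = 9 days. The other 29 − 16 = 13 of the 22 days are the Day 16 placebo day and follow-up.

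**Step 2: expected incidence with no drug effect.** Assumption, not in the documents: a constant background probability h of a first TEAE per subject-day, the same at every dose. Incidence = 1 − (1 − h)^T.

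| h per day | 0.05 mg (T = 1) | 0.1 mg (T = 1) | 0.2 mg (T = 4) | 0.5 mg (T = 22) |
|---|---|---|---|---|
| 1% | 1.0% | 1.0% | 3.9% | 19.8% |
| 2% | 2.0% | 2.0% | 7.8% | 35.9% |
| 3% | 3.0% | 3.0% | 11.5% | 48.8% |

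For example, 1 − 0.98^22 = 1 − 0.641 = 35.9%. Over the visit window, h = 2% gives 33.2% (T = 20) to 38.4% (T = 24). The 0.5 mg column is about 16 to 20 times the 0.05 mg column (48.8/3.0 to 19.8/1.0).

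**Step 3: how often this would show in one trial.** A binomial simulation used 34 subjects per column (Section 4; Section 5 says 32), columns treated as independent, 200,000 runs and no drug effect. It used the continuous form 1 − exp(−λT), which gives 19.7%, 35.6% and 48.3% for the 0.5 mg window at λ = 0.01, 0.02 and 0.03.

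| λ per day | 0.5 mg is the single highest | 0.5 > 0.2 > both lower doses |
|---|---|---|
| 0.005 | 88% | 31% |
| 0.01 | 97% | 52% |
| 0.02 | over 99% | 71% |
| 0.03 | over 99% | 81% |

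**Step 4: a single placebo column.** The SAP states no window, so one is assumed for illustration: Group 2A from Day 2 to Day 29 (27 days) and Group 2B from Day 1 to Day 16 (15 days). At h = 2%: [(1 − 0.98^27) + (1 − 0.98^15)]/2 = (42.0% + 26.1%)/2, about 34%. That is close to the 0.5 mg column (35.9%) and far above 2.0%, 2.0% and 7.8%.

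**Step 5: which remedy works.** Ending the 0.5 mg window at the Day 16 dose gives 1 − 0.98^9 = 16.6%, still about 8 times the 0.05 mg figure, so truncation alone is not enough. A placebo column cut at the same study days has the same expected incidence as CBP-307 in every window, so the expected difference is 0. The expected event rate per subject-day is also the same in every window.

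**The case against.** The strongest reply has four parts.

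- **The tables are descriptive.** Section 8.6.7 plans no inferential analysis, and all AEs are listed with onset and duration, so a missing table can be built later without loss of data. This is true and limits the severity. But with no test or interval, readers depend on the raw percentages.
- **Counting post-dose events under the last CBP-307 dose is a deliberate choice.** That stands. The point is to show those events separately, not to drop them.
- **Forced titration ties dose to study day, so no table can fully separate them.** That also stands. A windowed table supports drug versus concurrent placebo within each window, not a clean dose comparison.
- **The TFL shells, which are not shown, may add windows.** They may, but the SAP itself sets counting rules for CBP-307 alone.

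A reader might also infer more than the text supports. That no Group 1 versus Group 2 TEAE table will be produced is too absolute, because Section 6 says summaries follow planned sequences; the two sections conflict and need reconciling. That placebo is pooled over the whole stay is not stated; there is only a single label and the general window. Nor is it stated that moxifloxacin columns follow the last dose received. The last-dose sentence in Section 8.6.1 concerns onset time in listings, and the 0.5 mg rule itself departs from last-dose attribution after the Day 16 placebo.

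**Conclusion.** The point holds as a reporting weakness that is cheap to mend; it does not touch the primary QTc analysis. Time at risk differs about 22-fold between the lowest and highest CBP-307 doses, no matching control window is stated and no exposure adjustment is planned. Under a constant background of 1% to 3% per subject-day and no drug effect, the expected 0.5 mg incidence is about 20% to 49%, against 1% to 3% at each of the two lowest doses.

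A reader might conclude that the table is bound to show a dose-response. The documents do not support that. The size rests on an assumed constant rate, which could differ between confinement (to Day 19) and the outpatient period. The 0.05 and 0.1 mg windows are equal, so no gradient is expected between them. The full ordering appeared in only 31% to 81% of simulated null trials at the rates shown. What is well supported is that the 0.5 mg column would usually be highest from time at risk alone.

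It would also be too strong to say that nothing can be read against placebo. Under the illustrative placebo windows, 0.5 mg and placebo would be similar when there is no effect; the unfair comparison is with the three lower doses.

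**What to change.** Keep the planned tables and make these additions to Section 8.6.1:

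- Add a TEAE table by common study-day windows (Day 1; Day 2; Days 3 to 6; Days 7 to 15; Day 16 to end of study), with Group 1 beside concurrent Group 2. Show moxifloxacin-exposed subgroups separately: Group 2A from Day 1 and Group 2B from Day 16. On Day 1 the concurrent placebo is then Group 2B only.
- Show events during 0.5 mg dosing apart from post-treatment events.
- Give events per subject-day alongside the percentages.
- State the counting windows for placebo and moxifloxacin, and reconcile the by-treatment layout with the Section 6 sentence on planned sequences.

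The cost is one or two extra descriptive tables from AE and dosing dates already collected. A footnote should say that dose remains tied to study day by the titration.

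### The SAP promises the number of TEAEs, but its counting rule merges repeats of a preferred term within a subject and treatment, so the reported figure is not an event count

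*SAP*

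**What the plan says.** SAP Section 8.6.1 (Adverse Events) introduces its main summaries with "The frequency of subjects with TEAEs and the number of TEAEs will be summarized for the following categories". The categories are TEAEs and treatment-related TEAEs, each given overall, as serious, as leading to discontinuation, as leading to death, and by severity. The tables by system organ class and preferred term are different and report subjects only: "The frequency of subjects will be summarized separately for TEAEs and treatment-related TEAEs by the following".

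The same section then lists counting rules for TEAE summary statistics. The last one covers a subject with several TEAEs of one preferred term under one treatment and says that "this will be counted as 1 TEAE for that treatment under the maximum severity recorded".

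The CBP-307 windows in which TEAEs are attributed to a dose are also fixed there:
- 0.05 mg: "from the time of dosing 0.05mg on Day 1 until the start of dosing 0.1mg on Day 2"
- 0.1 mg: "from the time of dosing 0.1mg on Day 2 until the start of dosing 0.2mg on Day 3"
- 0.2 mg: "from the time of dosing 0.2mg on Day 3 until the start of dosing 0.5mg on Day 7"
- 0.5 mg: "from the time of dosing 0.5mg on Day 7 until study completion (Day 7~EOS"

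Section 4 (Study Design) puts the follow-up visit at Day 29 ± 2. Section 8.6.1 also has all AEs listed individually.

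**The concern.** Counting a subject once per preferred term, at worst severity, is a sound rule for a count of subjects. Here its unit is the TEAE, and it stands among rules for TEAE summary statistics in general. A programmer who follows the text would therefore merge separate episodes in the event column as well.

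Incidence and severity of AEs is a named safety endpoint (Section 3), and no inferential safety analysis is planned (Section 8.6.7). The descriptive tables are therefore the main summary of tolerability. A column labelled as a number of events that omits repeat events will be misread. The rule also does not say how a merged record is classed as serious or treatment-related when its component events differ.

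**Working it through.** The SAP gives no AE rate or expected event count, so there is no planned figure to reproduce. The check has two parts.

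**1. The text.** The event count is promised for the overall, serious, treatment-related and severity summaries. The merging rule covers TEAE summary statistics without restriction. Together they make the reported number the count of distinct subject × preferred term × treatment combinations. Two headaches in one subject at 0.5 mg, one mild and one moderate, would appear as one moderate event. The mild one would leave the severity table.

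**2. The size, under an assumption.** Inputs:
- Window lengths T from Section 8.6.1: 1 day (0.05 mg), 1 day (0.1 mg), 4 days (0.2 mg), and Day 7 to Day 29 = 22 days (0.5 mg; 20 to 24 days with the visit window).
- Recurrence rate r of one preferred term per subject-day: not in the SAP, so assumed at 0.01 to 0.10, as a Poisson process with the same rate in all subjects and on all days.
- 34 subjects in Group 1 (Section 4). Section 5 says 32, but the percentages do not depend on this.

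Expected events per subject = rT. Expected count under the rule = 1 − exp(−rT). Share lost = 1 − [1 − exp(−rT)]/(rT).

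Example at 0.5 mg with r = 0.05: rT = 1.1, and 1 − exp(−1.1) = 0.667. The share lost is 1 − 0.667/1.1 = 39.4% (36.8% to 41.8% for 20 to 24 days).

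| Window | T (days) | r = 0.01 | r = 0.02 | r = 0.05 | r = 0.10 |
|---|---|---|---|---|---|
| 0.05 mg; 0.1 mg | 1 each | 0.5% | 1.0% | 2.5% | 4.8% |
| 0.2 mg | 4 | 2.0% | 3.9% | 9.4% | 17.6% |
| 0.5 mg | 22 | 10.2% | 19.1% | 39.4% | 59.6% |

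For 34 subjects at 0.5 mg, all events against events counted under the rule are 7.5 against 6.7, 15.0 against 12.1, 37.4 against 22.7, and 74.8 against 30.2.

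**Placebo.** The SAP fixes no placebo window. Suppose it ran from Day 2 to Day 29 in Group 2A (27 days, 17 subjects) and from Day 1 to Day 16 in Group 2B (15 days, 17 subjects). At r = 0.05 the events number 17 × 0.05 × (27 + 15) = 35.7, and the rule counts 17 × 0.741 + 17 × 0.528 = 21.6, a loss of 39.6%. Over the four rates the loss is 10.5, 19.5, 39.6 and 59.3%, practically the same as at 0.5 mg.

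**The case against.** The strongest reply is that a prespecified, reproducible counting rule defines its own statistic, so the result is a convention and not an error. The table shells, which might label the column differently, are not shown. Incidence is naturally read per subject, and subject frequencies, the preferred-term tables and the listings are untouched. This limits the harm. It does not remove the mismatch, because Section 8.6.1 itself calls the statistic the number of TEAEs and sets it beside the number of subjects.

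A second reply is that the rule stops one worsening event from being counted twice, since the windows admit TEAEs that start or increase in severity. That is a fair concern, but the rule as worded also merges separate episodes.

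A reader might go further and infer that the rule biases the safety comparison in favour of the highest dose. The documents do not support this:
- Raw counts over windows of about 1, 1, 4 and 22 days are not comparable across doses under either rule. At r = 0.05 and 34 subjects the merged counts are about 1.7, 1.7, 6.2 and 22.7, and the full counts about 1.7, 1.7, 6.8 and 37.4. The 0.5 mg dose shows by far the most events either way, and full counting widens that gap at an identical daily rate.
- Against placebo, the inferred window loses about the same share.

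A reader might also cite a nine-fold understatement at 0.5 mg. That needs one subject to have a new, separately recorded episode of the same term on each of the nine dosing days from Day 7 to Day 15. Nothing in the SAP suggests such a rate.

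**Conclusion.** The point holds as a mismatch between a promised statistic and the rule that produces it. As written, the number of TEAEs is a count of subject-by-preferred-term-by-treatment combinations. It understates events whenever a term recurs within a treatment and removes milder repeats from the severity event counts.

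The percentages in the table are illustrations that rest on the assumed Poisson recurrence at a constant rate, not forecasts. The larger loss at 0.5 mg is shown only relative to the shorter CBP-307 windows and follows from window length. The error is confined to the event-count columns. It should be corrected before the tables are programmed, but it does not threaten the trial's main conclusions.

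**What to change.** State in Section 8.6.1 that the once-per-preferred-term, maximum-severity rule applies only to counts of subjects. For the number of TEAEs, count each distinct episode in its treatment window at its own severity. Where one continuing event worsens, count it once per window at its highest severity there, which avoids the double counting that the present rule prevents.

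If the sponsor prefers to keep the merged count, relabel it as a count of subject-by-preferred-term combinations in the SAP and the table shells.

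The first option costs a sentence or two and a small change to the event-count derivation. The second costs only wording. Neither makes raw counts comparable across windows of unequal length, and the tables should not be read as if it did.
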